9.8 Quality Control

All sites will be trained by phone on the protocol and study logistics.

The quality control procedures used for data management and statistical analysis will be described in the Data Management Plan and in the Statistical Analysis Plan.

9.9 Bias and Limits of the Study

The main bias identified in this survey is the selection bias.

Selection bias is a distortion of evidence or data that arises from the way that the data are collected.

The selection bias that could possibly occur in this study is related to the selection of the participating Physicians.

As inherent in all observational studies, the participation of Physicians is voluntary; some amount of selection bias will therefore be present as Physicians who are better informed may be more liable to participate in the survey.

Given that Physicians participating in pregnancy or safety registries are better engaged with Eurartesim[™] risk management activity, the list of approximately 300 Physicians per country, to be used for the present survey, will be separate from the list of Physicians involved in both pregnancy and safety registries.

To characterise the potential selection bias, information about Physicians (Specialty, geographic location, institution type, years in practice, number of malaria patients currently treated, number of patients treated with Eurartesim[™] the previous year, number of months since last patient treated with Eurartesim[™]) will be collected for all contacted Physicians, whether or not they participate in the study. Reasons for non-participation will also be collected. Characteristics of participating and non-participating Physicians will be compared.

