9.2.1.2 Sampling

Physicians will be selected among a list of approximately 300 physicians per country, provided by the Sponsor.

The following selection process will be conducted in each country respectively 12 months and 24 months after Physician received education material:

- A recruitment mail containing the study summary and a participation form will be sent to all Physicians.
- Physicians will be asked to send back the completed participation form to Mapi. Characteristics of physicians, and if applicable, reason for non participation will be collected on the participation form.

- Non-respondent Physicians will be contacted by telephone by Site Monitor Associates (SMAs), trained for this study, to know if they agree or not to participate in the survey and collect their characteristics, and if applicable, the reason for non participation.

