9.5 Study Size

Assuming that 20% of Physicians agree to participate in the survey, approximately 60 participating Physicians per country are expected.

As the analyses will mainly comprise calculations of percentages of correct answers, the expected precision obtained for a given percentage has been calculated using the following formula:

$$e = 1.96 \times \sqrt{\frac{p \times (1-p)}{n}}$$

where n =sample size, p =percentage and e =absolute precision.

The following table presents the precision expected with 60 participating Physicians, considering a two-sided confidence interval of 95% and expected percentages ranging from 10% to 50%.

	р				
	10%	20%	30%	40%	50%
Precision	7.6%	10.1%	11.6%	12.4%	12.7%
Note: This computation is based on large sample normal approximation					

For clarity, assuming for example an expected percentage equal to 30%, the two-sided 95% confidence interval will extend ±11.6% from the observed percentage.

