9.7 Data Analysis

The statistical analysis will be carried out using SAS software version 9.2.

It will be conducted for 12-month and 24-month surveys, separately, on data collected from all participating Physicians and for each country.

A Statistical Analysis Plan will be prepared by Mapi and approved by the Sponsor before the data-base is frozen.

Analytical methods

Continuous variables will be described by their mean, standard deviation, median, quartiles 1 and 3, extreme values (minimum and maximum) and the number of missing data.

Categorical variables will be described by the total and percentage of each response and the number of missing data. 95% confidence intervals will be computed on each individual percentage.

Description of the study population:

Characteristics of participating Physicians will be described.

To assess the representativeness of participating Physicians, characteristics of participating and non-participating Physicians will be compared. Reasons for non-participation will be described.

Response to the primary objective:

- Knowledge of indication of Eurartesim[™] will be described.
- Knowledge of prescription modalities of Eurartesim[™] will be described.
- Knowledge of administration modalities of Eurartesim[™] will be described.
- Knowledge of effects on cardiac repolarization will be described.
- Knowledge of high-risk patients will be described.
- Knowledge of potential side effects of Eurartesim[™] will be described.

Response to the secondary objectives:

- Awareness of the pregnancy and safety registries will be described.
- Awareness of available information sources regarding Eurartesim[™] will be described.

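### With 80% non-participation assumed, the protocol states only a comparison of characteristics, so the effect of its self-declared main bias on the primary percentages goes unmeasured

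*Protocol*

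**What the plan says.** **Participation.** Protocol 9.2.1.2: "Physicians will be selected among a list of approximately 300 physicians per country, provided by the Sponsor". Section 9.5: "Assuming that 20% of Physicians agree to participate in the survey, approximately 60 participating Physicians per country are expected".

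**Precision.** Section 9.5 gives a normal-approximation table for 60 physicians, from 7.6 points at 10% correct to 12.7 points at 50%. Its worked example, at 30%, says that "the two-sided 95% confidence interval will extend ±11.6% from the observed percentage".

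**Bias.** Section 9.9 calls selection bias the main bias and states that "some amount of selection bias will therefore be present as Physicians who are better informed may be more liable to participate in the survey". It keeps the survey list separate from the physicians in the pregnancy and safety registries. To characterise what bias remains, it says that specialty, location, institution type, years in practice, malaria caseload and experience with the drug "will be collected for all contacted Physicians, whether or not they participate in the study".

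**How those data arrive.** Section 9.2.1.2 gives two routes. For the mailing, "Characteristics of physicians, and if applicable, reason for non participation will be collected on the participation form". Physicians who do not respond are telephoned by trained staff, who ask whether they will take part and collect their characteristics and any reason for declining.

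**Use made of them.** Section 9.7 says that "characteristics of participating and non-participating Physicians will be compared" to assess representativeness, and that reasons for non-participation will be described. Knowledge is reported as percentages with 95% confidence intervals, for all participants together and for each country.

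**The concern.** The protocol expects four in five listed physicians not to take part and names a mechanism that would make participants look better informed than the list they come from. It plans to gather data on non-participants, but the only use it states is a side-by-side comparison. Such a comparison can show that the groups differ in, say, specialty or experience with the drug. It cannot show how far that difference moves the percentage of correct answers, which is the primary result.

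The survey was requested to assess whether physicians understand risk-minimisation material. If participants know more than the rest of the list, raw percentages would make the material look better understood than it is. A reader of 9.5 would see a margin of at most 12.7 points, with no note there that it leaves non-response out.

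**Working it through.** **1. The plan's own figures.** 300 × 0.20 = 60 participants per country, leaving 300 − 60 = 240 non-participants (80%). With e = 1.96 × √(p(1−p)/60):

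| p | 10% | 20% | 30% | 40% | 50% |
|---|---|---|---|---|---|
| Stated (points) | 7.6 | 10.1 | 11.6 | 12.4 | 12.7 |
| Recomputed (points) | 7.59 | 10.12 | 11.60 | 12.40 | 12.65 |

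The table is right. The formula contains sampling variance only.

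**2. Bias of a raw percentage.** Let P be the percentage correct among participants and P − d the percentage among non-participants. The list-wide percentage is 0.20 × P + 0.80 × (P − d) = P − 0.80 × d, so the raw figure P is too high by 0.80 × d. The protocol gives no d; the values below are assumptions.

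| Assumed d (points) | 5 | 10 | 20 |
|---|---|---|---|
| Bias (points) | 4 | 8 | 16 |

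The bias equals the worst-case half-width at d = 12.65 / 0.80 = 15.8 points, and the half-width of the 30% example at d = 11.6 / 0.80 = 14.5 points. For all three countries together, n = 180 and the half-width at 50% is 1.96 × √(0.25/180) = 7.3 points. With the same 80% non-participation, bias matches that at d = 7.3 / 0.80 = 9.1 points: pooling shrinks the interval but not the bias.

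**3. Effect on coverage.** Take P = 70% (assumed). The standard error is √(0.7 × 0.3/60) = 5.92 points. The chance that the nominal 95% interval contains the list-wide percentage is Φ(1.96 − b/SE) − Φ(−1.96 − b/SE), where b is the bias: about 90% at d = 5, 73% at d = 10 and 23% at d = 20.

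**4. Coverage of the characteristics.** The promise in 9.9 covers everyone contacted, while 9.2.1.2 offers a returned form or an answered call. Someone who gives neither supplies nothing, and no category is stated for that outcome. If 100%, 75%, 50%, 25% or 0% of the 240 non-participants supply data (assumed range), characteristics exist for 100%, 80%, 60%, 40% or 20% of the list; at 50%, for instance, (60 + 120)/300 = 60%. The abstract (4.4) describes the call only as asking about agreement, without the collection step, and 4.9 leaves out the comparison.

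**5. The pooled total.** As planned, each country contributes 60/180 = one third of participants and 300/900 = one third of the lists, so simple pooling and list-size weighting agree. They part only if participation or list size differs by country.

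**6. Price of weighting.** Weighted half-width = 12.65 × √(design effect). At assumed design effects of 1.25, 1.5 and 2 it is 14.1, 15.5 and 17.9 points.

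**The case against.** The objectives are descriptive, with no hypothesis test or success threshold. Section 9.9 sets out to characterise the bias and 9.7 to assess representativeness; a comparison of characteristics does both, so the plan does not contradict itself. Weighting is commonly left to the SAP, which is not shown. The 0.8 × d formula holds for any survey with 20% participation, and every d is the reviewer's choice. Weighting on specialty or location will not remove a bias that comes from being better informed unless those variables explain knowledge. All of this stands, and it limits the point to a supplementary analysis.

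A reader might infer more than the text supports:

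- **That non-respondents will give no data.** This is a prediction. Section 9.2.1.2 has trained staff telephone them to collect exactly these data. What holds is that full coverage is not assured.
- **That the characteristics are never used for correction.** Only the protocol is at hand; it states none, and the SAP may.
- **That the percentages are known to be too high.** Section 9.9 says better-informed physicians *may* be likelier to join, and it removes registry physicians, described as better engaged, from the list.
- **That refusers who give data resemble participants most.** This is plausible, but nothing in the protocol shows it.

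Deferral to the SAP does not dispose of everything. The coverage statement in 9.9 and the uncaveated precision in 9.5 are protocol text. Recruitment route and contact outcome have to be recorded during fieldwork, whereas the SAP need only be approved before the database is frozen.

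**Conclusion.** The point holds as a worthwhile, inexpensive improvement. It is not an error in any stated figure. On the protocol's own participation assumption, a raw percentage overstates list-wide knowledge by 0.8 points for every point by which participants outscore non-participants. At assumed gaps of 5 to 20 points that is 4 to 16 points, against a stated worst-case half-width of 12.7. Whether such a gap exists is unknown, and the stated analysis offers no way to gauge it, although the characteristics to be collected, including experience with the drug, would allow a partial check.

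The size rests on 20% participation and on assumed values of d. The pooling issue is small unless participation differs by country.

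**What to change.** **Section 9.7.** Keep the raw percentages as the primary estimates and add:

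- As a sensitivity analysis, percentages weighted for participation within country on the characteristics listed in 9.9, with robust 95% confidence intervals and the three-country total weighted by list size. Add sponsor-list variables only if they exist, since the protocol does not say what the list holds. Without them, the weights can speak only for physicians whose characteristics were obtained.
- A comparison of knowledge between physicians recruited by mail and those recruited by telephone, as an indirect check on volunteer bias.
- Separate counts of refusers with data, refusers without data and physicians never reached.

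Have the fieldwork forms record recruitment route and contact outcome from the start.

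**Section 9.9.** Limit the coverage statement to physicians who return the form or are reached, and align the abstract with 9.2.1.2 and 9.7.

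**Section 9.5.** Add one sentence saying that the tabulated precision covers sampling error only.

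**Cost.** Some wording, two recorded fields and one extra analysis. Weighted intervals will be wider (step 6 of the working), and weighting removes only the part of the bias that the measured characteristics explain. That is why it should stand beside the raw percentages and not replace them.

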10. PROTECTION OF HUMAN SUBJECTS

10.1 Ethical Conduct of the Study

The study should be conducted in compliance with the protocol, Good Epidemiology Practice guidelines, the ethical principles arising from the Declaration of Helsinki revised in 1989, and all current local laws, regulations, and practices.

10.2 Submissions

10.2.1 Ethics Committee (EC)

Ethical submissions will be performed as required by local legislation in each country involved in the study. The necessary ethical approvals will be obtained for each site before initiation of the site. The study is observational.

10.2.2 Institutional Review Board / Independent Ethics Committee Approval

Submissions and/or notification to the appropriate Institutional Review Board (IRB)/Independent Ethics Committee (IEC) will be performed as required by local legislation in each country for this type of study.

10.2.3 Data Protection

Physician's personal data shall be treated in compliance with all local applicable laws and regulations.

Data about participating Physicians will be declared and the Physicians will be informed – within the framework of their financial agreement – of their right to access, and correct these data as well as to object, on legitimate grounds, to the processing of these data.

When archiving or processing personal data pertaining to the Physician, the Sponsor shall take all appropriate measures to safeguard and prevent access to this data by any unauthorized third party.

10.3 Retention of Physician Records

When the study is completed, the Sponsor will maintain the data collected (questionnaires and databases) for 5 years.

11. MANAGEMENT AND REPORTING OF ADVERSE EVENTS/ADVERSE REACTIONS

11.1 Definitions

An **Adverse Event (AE)** is defined as any untoward medical occurrence in a patient administered a medical product and which does not necessarily have to have a causal relationship with this treatment. An adverse event can therefore be any unfavorable and unintended sign (for example, an abnormal laboratory finding), symptom, or disease temporally associated with the use of a medicinal product, whether or not the event is considered causally related to the use of this medicinal product.

An **Adverse Drug Reaction (ADR)** concerns noxious and unintended responses to a medicinal product. A reaction, in contrast to an event, is characterized by the fact that a causal relationship between the medical product and the adverse event is at least a reasonable possibility.

For regulatory reporting purposes on post approval safety data, if an AE is spontaneously reported, even if the relationship is unknown or unstated, it meets the definition of an ADR.

Serious AE/ADR (SAE/SADR):

Preamble: "Serious" and "Severe" are not synonymous. The term "severe" is often used to describe the intensity (severity) of a specific event; the event itself, however, may be of relatively minor medical significance (such as a severe headache). This is not the same as "serious", which is based on patient/event outcome or action criteria usually associated with events that pose a threat to a patient's life or functioning. Seriousness (not severity) serves as a guide for defining regulatory reporting obligations.

A serious adverse event or reaction is any untoward medical occurrence that at any dose:

- Results in **death** of the patient.
- Is **life-threatening:** this refers to an event/reaction in which the patient was at risk of death at the time of the event/reaction; it does not refer to an event/reaction which hypothetically might have caused death if it were more severe.
- Requires **in-patient hospitalisation:** an event/reaction that results in an admission to the hospital for any length of time. This does not include an emergency room visit or admission to an outpatient facility.
- Results in **prolongation of existing hospitalisation:** an event/reaction that occurs while the study patient is hospitalised and prolongs the patient's hospital stay.
- Is a **congenital anomaly/birth defect:** an anomaly detected at or after birth, or any anomaly that results in fetal loss.

- Results in **persistent or significant disability/incapacity:** an event/reaction that results in a condition that substantially interferes with the activities of daily living of a study patient. Disability is not intended to include experiences of relatively minor medical significance such as headache, nausea, vomiting, diarrhea, influenza, and accidental trauma (e.g. sprained ankle).
- Is a medically important event or reaction: an important medical event/reaction that may not be immediately life-threatening or result in death or hospitalisation, but based on medical judgment may jeopardize the patient and may require medical or surgical intervention to prevent any of the outcomes listed above (i.e. death of patient, lifethreatening, hospitalisation, prolongation of hospitalisation, congenital anomaly/birth defect, or persistent or significant disability/incapacity). Examples of such events include allergic bronchospasm requiring intensive treatment in an emergency room or at home, blood dyscrasias or convulsions that do not result in inpatient hospitalisation, or the development of drug dependency or drug abuse.
- Any suspected transmission via a medicinal product of an infectious agent is also considered a serious ADR.

Relatedness assessment

The Physician will use the following definitions for any adverse event and serious adverse events, to assess the relationship of the adverse event to the use of Eurartesim[™]:

- **Related:** An adverse event has a strong temporal relationship to study drug or recurs on re-challenge and another etiology is unlikely or significantly less likely or a more likely alternative etiology exists.
- Not related: An adverse event is due to an underlying or concurrent illness or effect of another drug and is not related to the study drug (e.g., has no temporal relationship to study drug or has a much more likely alternative etiology), or an adverse event has little or no temporal relationship to the study drug and/or a more likely alternative etiology exists.
- **Unassessable:** a reasonable judgment cannot be made (e.g., key information is missing)

Except for an adverse event which has a strong temporal relationship to study drug alternate etiology must be provided by the Physician for the adverse event.

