11.2 AE/ADR reporting

This study is not an organized data collection system on patients treated with Eurartesim[™]. No patients will be followed-up in this study. However and considering that the objectives of the study consists of measuring the effectiveness of risk management measures, this study qualifies as a PASS study with primary data collection from healthcare professionals.

Consequently and in accordance with EU Good pharmacoVigilance Practices (Modules VI and VIII), reports of ADRs suspected to be related to Eurartesim[™] should be reported to competent health authorities. Reports of adverse events should only be summarized in the study report.

During the study period, in the event the Physician is aware of a **serious** AE/ADR in a patient treated with Eurartesim[™], the Physician will notify the Corporate Drug Safety of Sigma-Tau **within 24 hours** of the Physician becoming aware of the event, using the SAE Form provided.

The completed and signed SAE form shall be sent to:

Sigma-Tau Corporate Drug Safety e-mail: [contact] [contact] Safety [contact]

Sigma-Tau will be responsible for contacting the reporting Physician to obtain any missing information on the SAE form, to allow it to conform with all international expedited reporting requirements.

It is the Physician's responsibility to report any serious adverse events related to products other than Eurartesim[™] to the respective marketing authorization holder and/or to the regulatory authorities as per local regulatory requirements.

Sigma-Tau pharmacovigilance will be in charge to report individual cases to the concerned health authorities.

Considering the objectives and the design of the study, the reporting of non-serious AE/ADR is not actively solicited in this study. However, and at his/her discretion during the study period, the physician can report suspected non-serious ADR to Eurartesim[™] to the Corporate Drug Safety of Sigma-Tau, using the same form and contact details as described above for serious AE/ADR.

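### Protocol 11.1 counts a more likely alternative cause towards both Related and Not related, and leaves one type of event that fits neither

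*Protocol*

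**What the plan says.** Protocol section 11.1 sets out three causality categories and says who applies them: "The Physician will use the following definitions for any adverse event and serious adverse events".

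- *Related* requires that the event "has a strong temporal relationship to study drug or recurs on re-challenge and another etiology is unlikely or significantly less likely". The sentence then runs on, so that its ending reads "another etiology is unlikely or significantly less likely or a more likely alternative etiology exists".
- *Not related* has two limbs. The first attributes the event to another illness or drug, with the example that it "has no temporal relationship to study drug or has a much more likely alternative etiology". The second is satisfied by "little or no temporal relationship to the study drug and/or a more likely alternative etiology exists".
- *Unassessable* applies when no reasonable judgement is possible. Missing key information is given as an example.

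A closing sentence adds: "Except for an adverse event which has a strong temporal relationship to study drug alternate etiology must be provided by the Physician".

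Earlier in the same section, an adverse drug reaction (ADR) is an event for which "a causal relationship between the medical product and the adverse event is at least a reasonable possibility".

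Section 11.2 sends ADRs suspected to be related to the drug to the health authorities. For the rest it says: "Reports of adverse events should only be summarized in the study report". Separately, it requires the physician to notify the sponsor's drug safety unit of any serious event or reaction within 24 hours. It makes the sponsor's pharmacovigilance function responsible for reporting individual cases.

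**The concern.** A causality scale works only if its categories exclude each other and together cover every case on which a judgement can be made. Here one clause serves two opposite categories, so two physicians with identical facts can choose opposite ratings and both be following the protocol. In addition, *Related* demands more than the ADR definition in the same section, so an event can be a reasonable-possibility ADR and yet have no category.

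The rating has a use. Section 11.2 describes the survey as a PASS (post-authorisation safety study) and treats suspected-related ADRs and other adverse events differently. A contradictory rating rule can therefore affect which group a case is placed in.

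**Working it through.** No arithmetic applies; the check is a logical comparison of the definitions in section 11.1. Section 5 states that this is the original protocol, so the wording is current text.

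Notation: T = strong temporal link; R = recurs on re-challenge; U = another cause is unlikely or less likely; M = a more likely alternative cause exists; L = little or no temporal link.

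**Not related, second limb.** The connective is and/or, so either condition is enough: L or M.

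**Related.** The sentence chains *and* and *or* without brackets. Four groupings are plausible. *Not related* is met in both columns, because M alone satisfies it.

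| Grouping of *Related* | T and M both true | M true, T and R false |
|---|---|---|
| (a) (T or R) and (U or M) | met | not met |
| (b) ((T or R) and U) or M | met | met |
| (c) T or (R and (U or M)) | met | not met |
| (d) T or (R and U) or M | met | met |

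**Overlap.** With a strong temporal link and a more likely other cause, both definitions are met under all four groupings. Under (b) and (d) the overlap extends to any event with a more likely other cause, even without a temporal link. No sentence says which category prevails. The closing sentence does not separate them either: it waives the statement of another cause for events with a strong temporal link, which is where the two categories collide.

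**Gap.** Take an event with plausible but not strong timing, no re-challenge recurrence and no more likely other cause: T, R, L and M are all false.

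- *Related* fails under (a) to (d), whatever U is.
- *Not related* fails on its second limb because L and M are false. It fails on its first limb because there is no better explanation to attribute the event to.
- *Unassessable* does not apply if the physician can form a judgement.
- The ADR definition asks only for a reasonable possibility of causation, not strong timing, so the event can still be an ADR.

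**What deleting the clause achieves.** What remains of *Related* is T or R and U, which can be grouped in two ways.

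- (T or R) and U: if M is true then U is false, so the overlap on M disappears.
- T or (R and U): T with M still meets both definitions.

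Deletion therefore removes the overlap only if the condition on other causes is made to govern both timing and re-challenge. It does not close the gap, because the gap event has M false and never depended on that clause.

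**The case against.** The best case on the other side is that little follows from this. Every serious event or reaction goes to the sponsor within 24 hours, with no rating as a precondition. The sponsor, not the rating physician, reports individual cases. The ADR definition stands on its own, and section 11.2 nowhere says that the physician's category alone decides the route. Non-serious reports are not actively solicited and are left to the physician's discretion. The study is a survey of physician knowledge that follows no patients, and the data analysis section (9.7) lists no adverse-event analysis. All of this is correct and limits the consequence: receipt of serious cases is not at risk, and neither are the objectives, the percentages or the stated precision.

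It does not remove the contradiction. The physician is told to apply these definitions to every adverse event, two of them can be met at once, and nothing resolves the tie. Section 11.1 does treat a spontaneously reported event as an ADR when the relationship is unknown or unstated. That does not cover an event that a physician has actively rated *Not related*.

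It can also be said that *Unassessable* absorbs the gap. It does so only where no reasonable judgement can be made. Missing information is merely an example of that condition, so its absence does not by itself rule the category out; but the gap remains wherever a judgement is possible.

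**Conclusion.** The rule is wrong as written and should be fixed. The overlap for an event with a strong temporal link and a more likely other cause holds under every reading tried. The gap holds for the specific event described, on the assumption that the physician can form a judgement. The effect is on the causality rating and, through it, possibly on whether a case is treated as a suspected-related ADR or only summarised. The protocol gives no expected number of events, so its size cannot be stated as a rate.

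Four stronger conclusions that a reader might draw are not supported:

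- *That the physician's choice of category alone decides whether a case reaches the authorities.* The 24-hour rule, the sponsor's reporting role and the separate ADR definition all stand between the rating and that outcome.
- *That every event with a more likely other cause carries both labels.* This holds under two of the four groupings only.
- *That every event with plausible but not strong timing has no label.* If a more likely other cause exists it is *Not related*; if it recurs on re-challenge and another cause is unlikely it is *Related*. Only the remainder is uncovered.
- *That section 11.1 already makes all Unassessable cases ADRs.* The sentence in question concerns spontaneous reports, whereas section 11.2 describes this study as primary data collection.

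**What to change.** In section 11.1:

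1. Delete the final clause of *Related*, the one about a more likely alternative cause.
2. Bracket or reword what remains so that the condition on other causes applies to both the timing and the re-challenge criteria.
3. Reconcile *Related* with the ADR definition already in the section, so that an event with a reasonable possibility of causation but less than strong timing has a category. Then check the redrafted categories against combinations of timing, re-challenge and other causes, to confirm that none fits two categories and that none on which a judgement is possible fits none.
4. Check that the SAE form, which is not shown, carries the same wording.

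The cost is a one-paragraph protocol correction and, if needed, a matching change to the form. The questionnaire, study size and planned analyses do not change.
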